Zimmer Biomet offers a Hip Screw technology that is capable of delivering a Bone Substitute Material (BSM) to the fracture-implant interface for fixation of fractures of the femoral neck [5][6]. This device allows hard setting BSM to the precise location, providing a multi-dimensional fixation that is critical to reduce the chance of joint collapse and articular fragment displacement and ultimately could reduce the high reoperation rates reported for this kind of injury.

This study will assess the reoperation rates, including revision, and document the clinical and radiographic outcomes of hip fracture patients, utilizing the N-Force Fixation System. Results will be compared to “standard” non-augmented cannulated screw (historic control).

IV. Study Objectives

The objective of this prospective study is to assess safety and performance of N-Force Screws augmented with N-Force Blue applied in intracapsular proximal femur fracture treatment. Further results will be compared to non-augmented standard cannulated screws (historic control).

Safety: Will be assessed by monitoring the frequency and incidence of adverse events (AE), serious adverse events (SAE), adverse device effects (ADE), serious adverse device effects (SADE), and unanticipated serious adverse device effects (USADE) and device deficiencies.

Performance: Will be determined by analyzing the fracture healing (union) rate at 6 weeks, 3 months, 6 months, and 12 months postoperatively.

The primary endpoint of this study is defined as re-operation within 12 months after initial surgery. Reoperation is defined as a second surgery to correct the previous procedure or the complications of a previous surgery. For this study, reoperation will include second surgeries to promote fracture healing, relieve pain, treat infection, or improve function including:

- Removal of the implant prior to fracture healing
- Internal fixation with another implant during revision surgery
- Revision to total hip arthroplasty
- Incision and drainage or other soft tissue procedure due to deep infection at the bone implant interface.

Secondary endpoints of this study include:

- Clinical (FIX-IT) and radiologic (RUSH)^{[8][9]} fracture healing at 6 weeks, 3, 6 and 12 months post-surgery.
- Length of femoral neck ^{1.a.[7]}
- Proportion of patients with avascular necrosis at one year FUP (Steinberg classification)
- Functional Index for Trauma (FIX-IT)^[10]
- Harris Hip Score^[11]
- Timed “Up-And-Go” Test^[12]
- EQ-5D-5L

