with the subject. Patients who have previously received N-Force Screws augmented with N-Force Blue may be enrolled in the study if informed consent occurs prior to the end of the 6 weeks follow-up visit window. This will include retrospective chart review for pre-operative and operative data for patients who meet the inclusion criteria (and do not meet any of the exclusion criteria) and have available surgical data. Patients that meet these requirements will be asked to consent to study participation postoperatively. The consented patients will be followed prospectively at designated follow-up visits if all appropriate Ethics Committee approvals and patient consent is obtained. The post-operative clinical and radiographic evaluations will be conducted at 6 weeks, 3 months, 6 months, and 12 months post-surgery.

Review of radiographs will be completed by the investigators at each clinical follow-up interval to determine the incidence of loss of reduction, implant migration and radiographic evidence of fracture healing. In addition, the Investigator will review radiographs at each clinical follow-up interval to ensure radiographic evidence of adverse events is documented and reported to the IRB or EC and the Sponsor as required. At the Sponsor's discretion, the Sponsor may request copies of these radiographs for independent radiologic review. The Sponsor may request one central reviewer for all radiographs independent of the surgeon and institution.

VI. Study Population

The study population for primary statistical analysis will be comprised of males and females who require intracapsular proximal femur fracture repair and satisfy the inclusion/exclusion criteria outlined in this section of the protocol. In total, one-hundred-and-ninety (190) patients will be enrolled.

In order to avoid potential selection bias, each Investigator will offer study participation to each consecutive eligible patient presenting as a candidate for intracapsular femur fracture repair using the commercially available (FDA cleared) N-Force Screws augmented with N-Force Blue. Eligible candidates who express interest in study participation will be offered Informed Consent. The **Inclusion/Exclusion Criteria** case report form should not be completed until the study-specific consent form has been completed.

1. Inclusion Criteria

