After completing the Informed Consent process, candidates who agree to enter the study must sign and date the IRB or EC approved Informed Consent. The Informed Consent must be signed and dated prior to the date of the study surgery for prospective subjects. Subjects enrolled retrospectively may sign and date the Informed Consent after surgery.

A copy of the signed Informed Consent must be provided to the study subject. The original signed Informed Consent is to be filed in the subject's medical record, study subject binder, or regulatory binder.

Study data will not be collected until the Informed Consent has been signed and dated. If the candidate does not wish to participate (does not sign and date the Informed Consent), data for that candidate will not be collected for this study.

C. Informed Consent / Enrollment Log

An **Informed Consent / Enrollment Log** (Appendix C) will be maintained at the site throughout the course of the study. The purpose of the log is to provide documentation that all enrolled study subjects underwent the Informed Consent process, signed and dated the IRB or EC approved Informed Consent, and were provided with a copy of the fully executed consent with all required signatures. All candidates who sign and date the approved Informed Consent for the study must be entered in the log. If a subject signs and dates additional Informed Consent(s) after enrollment (e.g., due to a protocol amendment, protocol

revisions, etc.), subsequent signings will also be recorded in the log. The Informed Consent/Enrollment Log will be filed in the site Regulatory Binder for the study. After a subject receives the study device during surgery, the date of surgery will be added to the log. The subject will now be considered an active study subject. In the event that a subject does not receive the study device at the time of surgery, a **Study Completion** case report form must be submitted and this will be documented as a screen failure on the Informed Consent/Enrollment Log.

D. Subject Enrollment

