Once the Informed Consent has been signed and dated by the subject or delegated signatory, the subject will be considered enrolled in the study. A unique case identification number (Case ID) will be assigned to each participating subject/femur (bilateral subjects will be assigned a unique case ID number for each femur). This unique case ID number will be used throughout the study for identification. Case ID numbers will be assigned consecutively in ascending order per site, with the starting number for a given site defined by the Sponsor. In the event that the subject does not receive the study device at the time of surgery, the subject will be considered a screen failure and documented on **the Informed Consent/Enrollment Log** (see above).

E. Monitor Log

The **Site Monitoring Visit Log** (Appendix C) will be maintained throughout the course of the study. The log will contain the visit date, monitor name/signature and the purpose of the visit (i.e. site initiation, onsite interim monitoring (as applicable), site close-out, etc.). The site monitoring visit log will be filed in the site Regulatory Binder for the study.

F. Delegation of Authority (Site Signature Log)

A **Delegation of Authority/Site Signature Log** (Appendix C) will be maintained throughout the study and will contain the names, initials, signatures and study responsibilities of all site personnel/designees involved in study procedures and data collection. This log will be filed in the site Regulatory Binder for the study.

G. Baseline/Pre-operative Assessment

Baseline/pre-operative data will be collected on the following case report forms at the time of enrollment:

1. Informed Consent

2. Inclusion/Exclusion Criteria
3. Demographic Evaluation
4. Adverse Event Report(s) (as applicable)
5. Protocol Deviation(s) (as applicable)

H. Surgical Technique

Standard operative procedures will be followed and all surgical procedures will be performed under aseptic conditions. Investigators will implant all commercially available N-Force Screws with N-Force Blue and any other compatible products in compliance with corresponding labeling requirements and in accordance with appropriate surgical technique(s).

I. Surgical, Immediate Post-surgical Procedures and Discharge (Data Collection)

Surgical and immediate post-surgical data will be collected on the following case report forms:

1. Operative and Surgical Device Information
2. X-rays (AP and Lateral)
3. Postoperative Discharge Assessment

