4. Adverse Event Report(s) (as applicable)
5. Protocol Deviation(s) (as applicable)
6. Implanted Device Form (as applicable)
7. Study Completion (as applicable)

J. Post-surgical management

Post-surgical management for study subjects will follow the investigator's standard of care for patients undergoing intracapsular proximal femur fracture. Post-surgical rehabilitative therapy will be as prescribed by the investigator.

K. Post-operative Follow-up Procedures (Data Collection)

Post-operative clinical evaluations/assessments will be conducted at 6 weeks \pm 14 days, 3 months \pm 30 days, 6 months \pm 60 days, and 12 months \pm 90 days post-surgery. The following case report forms will be collected at each interval:

1. Postoperative Follow-up
2. X-rays (AP and Lateral)
3. Physician Radiograph Assessment including RUSH

4. Steinberg Classification (12 months Follow-Up only)

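### The screen-failure rule does not separate a device never tried from one tried and abandoned, so device-exposed subjects can leave follow-up and the performance denominator

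*Combined protocol and SAP*

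**What the plan says.** Section VIII.D fixes enrolment at consent: "Once the Informed Consent has been signed and dated by the subject or delegated signatory, the subject will be considered enrolled in the study". For prospective subjects, Section VIII.B places that signature before the date of surgery.

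Section VIII.C makes active status depend on the operation: "After a subject receives the study device during surgery, the date of surgery will be added to the log. The subject will now be considered" (the sentence goes on to confer active status). For a subject who does not get the device, the Study Completion "case report form must be submitted and this will be documented as a screen failure on the Informed Consent/Enrollment Log". Section VIII.D repeats the rule: if the subject "does not receive the study device at the time of surgery, the subject will be considered a screen failure".

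Three other places bear on this:

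- Section IV puts adverse device effects of every grade within the safety objective, ending with "unanticipated serious adverse device effects (USADE) and device deficiencies". The adverse device effect definition in Section IX.E covers problems of implantation and any malfunction.
- Section VI gives the only population statement: "The study population for primary statistical analysis will be comprised of males and females who require intracapsular proximal femur fracture repair" and who meet the eligibility criteria. It mentions neither implantation nor screen failures.
- Section VIII.I lists, for the surgical stage, "Adverse Event Report(s) (as applicable") and a Study Completion form. The Section II table also shows an Explanted Device form, as applicable, in the operative and discharge column.

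**The concern.** A screen failure is normally someone found unsuitable before exposure. Here the label is applied after enrolment, on the basis of something that happens in the operating room. Two different subjects can receive it: one for whom the surgeon chose another treatment before opening the device, and one in whom a study screw was inserted or bone substitute injected and then abandoned. The second has been exposed, and the reason for abandoning the device may itself be a device deficiency or an adverse device effect.

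If the second kind of subject exits at surgery, the 12-month results describe only patients in whom implantation succeeded. Exclusion would then depend on device performance, which tends to flatter the device. The study is a single arm set against a fixed historical rate of about 15%, so a handful of subjects can matter. No comparison arm would lose subjects in the same way.

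**Working it through.** **1. What happens to an attempted-and-abandoned subject under the text.**

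| Step | Section | Consequence |
|---|---|---|
| Consent signed | VIII.D | Enrolled |
| Device tried, then replaced by another implant | VIII.C, VIII.D | Receipt is undefined; on a natural reading, not received |
| Classification | VIII.C, VIII.D | Screen failure, with a Study Completion form |
| 12-month visit | VIII.C, VIII.K | Never an active subject; data collection ends with study completion |
| Performance denominator | XI.B | Cannot be among the 151 evaluable at 12 months |
| Safety denominator | IV, VI, XI | No safety or treated set is defined, so undetermined |

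The retrospective route in Sections V and VI has the same selection, since it admits only patients who have already received the device.

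**2. The plan's own sample size.** Section XI.B gives a historical rate p0 = 0.15, an assumed rate p1 = 0.075, 151 evaluable subjects, 20% loss and 190 enrolled. It states no alpha, sidedness or power. Assuming two-sided 0.05 and 80% power:

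n = [(1.960 × √(0.15 × 0.85) + 0.842 × √(0.075 × 0.925)) / 0.075]² = [(1.960 × 0.3571 + 0.842 × 0.2634) / 0.075]² ≈ 150.97, so 151.

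151 / 0.8 = 188.75, so 189, against 190 planned. The figure reproduces, and it does not depend on the screen-failure rule.

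**3. How many added failures would matter.** Assumptions, none of them from the protocol: 11 reoperations in 151 (7.3%, close to the assumed 7.5%); success means an exact (Clopper-Pearson) two-sided 95% upper limit below 15%; and each of k abandoned attempts is added to both numerator and denominator, (11 + k)/(151 + k).

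| k | Result | Rate | Exact upper limit | Below 15%? |
|---|---|---|---|---|
| 0 | 11/151 | 7.3% | 12.7% | Yes |
| 1 | 12/152 | 7.9% | 13.4% | Yes |
| 3 | 14/154 | 9.1% | 14.8% | Yes |
| 4 | 15/155 | 9.7% | 15.5% | No |
| 5 | 16/156 | 10.3% | 16.1% | No |

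The denominator has to move with the count. With n held at 151, the last passing result is 13/151 (8.6%, upper limit 14.3%) and 14/151 fails (15.1%). That comparison would wrongly suggest that three added failures are enough.

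**4. The same question as an error rate.** With 151 implanted subjects, the rule in step 3 passes at 13 or fewer events. Suppose the failure rate over all attempts is truly 15% and a fraction f of attempts is abandoned and excluded. The rate among implanted subjects is then (0.15 − f)/(1 − f).

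| f (assumed) | Rate among implanted | Chance of passing |
|---|---|---|
| 0 | 15.0% | 0.014 |
| 1% | 14.1% | 0.028 |
| 2% | 13.3% | 0.053 |
| 3% | 12.4% | 0.096 |
| 5% | 10.5% | 0.270 |

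Steps 3 and 4 both count an abandoned attempt as a failure, which the protocol's endpoint does not do.

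**The case against.** A reader might infer that the rule removes intra-operative device failures from the safety results. The documents do not support that. No section says that screen failures are left out of safety summaries. These subjects are enrolled and logged, adverse-event and explant forms are available at the operative stage, and Section II requires a Product Experience Report for a device-related adverse event. Nothing in Sections VIII.C or VIII.D switches these off. What remains is narrower: the forms are completed as applicable, and collecting a form does not put a subject in a denominator when no analysis set is defined.

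A reader might also infer that the rule deletes primary events. It does not. Section IV defines reoperation as a second surgery, so changing implant during the index operation is not an event. What is lost is the subject's place in the denominator and any later reoperation. A later reoperation on a different implant would not clearly measure this device, which is a fair reason to leave the endpoint as it is.

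It can further be argued that a patient in whom a screw was inserted or substitute injected has received the device, so that the rule reaches only patients treated by another method. That reading is possible, but the text does not settle it, and sites could classify the same case differently.

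Finally, this is a post-market study of a cleared device with descriptive reporting, and implanted-only performance results are common. That limits the importance of the point, but it is not a reason to leave the status of exposed subjects open.

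**Conclusion.** The concern holds as a gap with a predictable direction. As written, the rule allows device-exposed subjects to leave follow-up and the performance denominator depending on intra-operative device performance, and nothing ensures that they stay in the safety denominator. It does not show that safety data are discarded or that primary events are lost.

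The size is unknown, because the documents give neither an intra-operative failure rate nor a success rule. Under the assumptions in the working, from a start of 11/151, three added failures leave the upper limit below 15% and the fourth takes it above. The stated sample size is unaffected.

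**What to change.** Amend the protocol as follows:

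- **Sections VIII.C and VIII.D:** define receipt of the device, and limit screen failure to subjects in whom no study screw or bone substitute was attempted.
- **Section XI:** define a safety set of all subjects in whom use was attempted. Keep attempted-but-not-implanted subjects in it, with adverse-event and device-deficiency reporting and follow-up, and report their number and reasons.
- **Section XI:** add a sensitivity analysis of the primary result that counts these subjects as failures in both numerator and denominator. Label it as going beyond the second-surgery endpoint, which stays unchanged.
- **Study Completion form:** it already asks for a reason; add a category for attempted and abandoned use.

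The cost is a few sentences, one form category and follow-up of a few more subjects. The safety figures may look slightly less favourable. Neither surgical care nor the planned sample size changes. This is a cheap improvement.

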5. EQ-5D-5L
6. FIX-IT
7. Timed “Up and Go” Test
8. Harris Hip Score
9. Adverse Event Reports(s) (as applicable)
10. Protocol Deviation(s) (as applicable)
11. Implanted Device Form (as applicable)
12. Study Completion (as applicable)

Subjects will be followed post-operatively for 12 months. Unless the study is otherwise closed, data will continue to be collected until the subject completes the study per the protocol, voluntarily withdraws from the study, is withdrawn from the study by the investigator, is lost to follow-up, undergoes revision to remove a study device (due to complication), or expires. See Management of Incurrent Events (Section IX, Subsection D of this protocol) for additional details. Reason(s) for study completion must be documented on the Study Completion case report form.

L. Minimization of Subjects Lost to Follow-up

Subject follow-up is extremely important for the conduct of a clinical study, and the expectation is to maintain the highest possible rate of follow-up compliance throughout this study. During the informed consent process and at each follow-up interval, subjects should be counseled on the importance of completing future study follow-up intervals.

M. Radiographic Definitions and Methods

All postoperative radiographic evaluations performed according to the protocol will be reviewed by the Investigator at the time of the evaluation and documented using the **Physician Assessment of Post-op Radiographs** case report form. This includes documentation of any significant radiographic findings. In addition, an **Adverse Event** case report form must be completed for those findings indicated by an asterisk on the **Physicians Assessment of Post-op Radiograph** case report form, or for any other findings identified as an adverse event.

[figure not shown]
o **Method to derive the length of the femoral neck:**

1. Draw a line along the femoral shaft axis.
2. Draw a line along the femoral neck axis.
3. Measure the distance CD (blue line) in millimeter.
4. Measure the distance AB (red line) of the **inferior** screw in millimeter.

[figure not shown]
To adjust for x-ray magnification the actual length of the femoral neck will be calculated using the following formula:

$$\text{Length of the femoral neck [mm]} = CD_{\text{measured}} \times \frac{AB_{\text{true}}}{AB_{\text{measured}}}$$

$$AB_{\text{true}} = \text{Known screw length [mm]}.$$

[figure not shown]

- **Non-union definition:** A total RUSH score below 18 at six month post-surgery is considered a non-union [9].
 - RUSH scoring examples:

	Cortical Bridging	Cortical Fracture Line Disappearance
Anterior	1	2
Posterior	1	1
Medial	1	1
Lateral	1	1
Total:	4	5

Trabecular Consolidation	1
Trabecular Fracture Line Disappearance	1
RUSH Total:	11

	Cortical Bridging	Cortical Fracture Line Disappearance
Anterior	3	3
Posterior	2	2
Medial	2	2
Lateral	3	3
Total:	10	10

Trabecular Consolidation	3
Trabecular Fracture Line Disappearance	3
RUSH Total:	26

1. Required radiographic views

Standing anteroposterior (AP) (a supine AP view will be accepted if the patient is unable to stand), and standard lateral radiographs of the operative femur are required to be captured at the pre-op, operative/post-op, 6 weeks, 3 months, 6 months, and 12 months post-surgery.

Radiographs should have similar exposure and must show the entire study device and surrounding bone. For consistency, every effort should be made to capture all radiographic views for a given subject using the same institution throughout the study. However, radiographs captured at a different institution may be used for the study, provided they meet required study specifications and are captured within the required interval window. The investigative site will retain copies (hard copy/CD/digital) of all radiographs referenced for the study.

2. Submission to Sponsor

At the Sponsor's discretion, study radiographs may be requested from the sites for independent radiographic review and assessment of appropriate parameters.

N. Recommended Revision Procedure

See Management of Incurrent Events (Section IX, Subsection D of this protocol)

IX. Reporting

The management of all study data received by the Sponsor will be the responsibility of the Sponsor or its Designee. The use or disclosure of all protected health information will comply with the Health Insurance Portability and Accountability Act (HIPAA). All information will be treated with strict adherence to professional standards of confidentiality and will be filed by the Sponsor under adequate security and restricted accessibility by clinical personnel. All electronic systems used to create, modify, maintain, or transmit study records will be validated according to 21 CFR Part 11(ii). Reports and communications relating to study subjects will typically identify each subject only by the subject's initials, assigned study subject Case ID number, date of surgery, operative side, and date of birth.

A. Prior to Initiation of the Study

1. Clinical Trial Agreement (CTA)

A fully executed (signed by all required parties) CTA must be on file with the Sponsor prior to any investigator participating in this study.

2. Institutional Review Board/Ethics Committee Protocol Approval

This study protocol must be submitted to and approved by the Investigator's Institutional Review Board (IRB) or Ethics Committee (EC). A copy of the IRB or EC approval letter must be submitted to the Sponsor. The letter should identify the following:

- Protocol name and/or number
- Date of IRB or EC meeting (if available)
- Date of approval
- Date of expiration
- Signature of IRB or EC

3. Informed Consent

A Sponsor-approved Informed Consent template (Appendix A Sample) will be provided along with the study protocol for IRB or EC submission and approval. If the IRB or EC requires revisions to the provided Informed Consent, the requested revisions must be submitted by the Investigator to the Sponsor for review and approval. Once the Sponsor has reviewed and

approved the revision, the Informed Consent will be re-submitted to the IRB or EC for final review and approval. A copy of the final IRB or EC approved Informed Consent form (ICF) must be submitted to the Sponsor.

4. ClinicalTrials.gov Registration

The Sponsor will be responsible for registering this study on www.ClinicalTrials.gov if required by local and national regulations.

B. Clinical Data Collection/Submission

1. Summary of Case Report Form Data Collection

- a. Study data will be collected on source documents which may include study-specific worksheets provided by the Sponsor. For subjects having bilateral intracapsular proximal femur fracture treatment, separate case report forms must be completed for each operative side.
- b. The following source document/CRF completion guidelines should be followed:
 - i. Complete carefully and accurately.
 - ii. Complete header information consistently across all case report forms for each individual study subject (when study-specific CRFs are used).
 - iii. Be sure that data on the source documents match that which is entered through the electronic data capture (EDC) system
 - iv. Use the study subject's unique Case ID number assigned as instructed. Do not provide information that is not requested on the CRFs.
 - v. Ensure that all fields are completed. For fields completed by the subject, efforts should be made to obtain any missing responses prior to the subject completing their visit.

2. Data Submission

- a. Completed CRFs will be submitted directly to the Sponsor by electronic data capture and submission via a method approved by the Sponsor. Every effort must be made to ensure data submission to the Sponsor is made within 30 days of the visit completion.

3. Quality Assurance of Data

- a. The Investigator should ensure the accuracy, completeness, legibility, and timeliness of the data reported to the Sponsor in the

CRFs and in all required reports. Data reported on the CRF, which are derived from source documents, should be consistent with the source documents or the discrepancies should be explained. All electronic systems used to create, modify, maintain, or transmit electronic study records will be validated according to 21 CFR Part 11⁽²⁾. The Sponsor will maintain quality control systems, in accordance with the Sponsor's policies and procedures.

C. Reporting Requirements

1. Investigator Reporting Responsibilities

The Investigator should ensure the accuracy, completeness, legibility, and timeliness of data reported to the Sponsor in accordance with this protocol. The Investigator or Designee will provide periodic reports to their IRB or EC as required to maintain IRB or EC approval throughout the study, and will provide any required final reporting to the IRB or EC upon study completion/termination. A copy of all IRB or EC re-approval letters must be submitted to the Sponsor. If the IRB or EC terminates or suspends its approval of the study, the Investigator or Designee will suspend study-related activities and will promptly notify the Sponsor. The Investigator should also promptly provide written reports to the Sponsor and the IRB or EC regarding any changes significantly affecting the conduct of the study, and/or increasing risk to the subjects.

2. Retention of Records

Study records must be retained by the Investigator or Designee for a minimum of 2 years from the Investigator's study termination date, or per applicable regulatory and/or IRB or EC requirements (whichever time period is greater). Measures shall be taken to prevent accidental or premature destruction.

D. Management of Incurrent Events

1. Failure to Obtain Informed Consent

Study data will not be collected until the Informed Consent has been signed and dated by the candidate. If a candidate does not wish to participate (does not sign and date the Informed Consent), data for that candidate will not be collected for this study.

2. Adverse Events

An adverse event is any unfavorable or unintended sign, symptom, or

disease that impacts the subject. Adverse event is synonymous with complication or medical event.

See Section IX, Subsection E of this protocol for additional information regarding adverse event classifications. Femur related, serious, and unanticipated events are required to be reported on the **Adverse Event Report** case report form. The completed **Adverse Event Report** case report form must be submitted to the Sponsor in a timely manner. The Investigator or Designee will also promptly provide the Sponsor with any additional requested information required for the Sponsor to comply with regulatory requirements. If applicable per their reporting requirements, the Investigator or Designee will also report applicable adverse event(s) to their IRB or EC.

3. Revision

In the event that removal of one or more of the study related components is necessary (due to complication), the Investigator will determine the best treatment and/or revision method for the subject.

Prior to revision surgery, the Investigator or qualified Designee must document any significant radiographic findings related to the need for revision on the **Physician Assessment of Postop Radiographs** case report form. An **Adverse Event** case report form must be completed for those findings indicated by an asterisk on the **Physicians Assessment of Postop Radiograph** case report form.

Once the revision surgery has been completed, the Investigator or qualified Designee must complete an **Adverse Event Report** case report form as well as a **Study Completion** case report form terminating the subject from the study. For the study completion status, select “Study Device Removed”. This procedure also applies to partial revisions e.g. removal of one of the three screws.

4. Investigator Withdrawal

The Investigator can choose to withdraw a subject from the study if the subject no longer meets study inclusion/exclusion criteria. The reason for the Investigator’s withdrawal of the subject must be documented on the **Study Completion** case report form.

5. Subject Withdrawal

Study subjects may choose to withdraw from the study at any time, for any reason. If possible, a final evaluation will be completed for any subject who no longer wishes to participate in the study. The reason for the subject withdrawal must be documented on the **Study Completion** case report form.

6. Lost to Follow-up

A study subject will be considered lost to follow-up after they have missed a visit and a reasonable number of attempts to locate and evaluate them have failed. All attempts to contact the subject are to be documented in the subject's medical record and on the **Study Completion** case report form. In particular, the reason for the Study Completion must be documented. Missed visit(s) also must be documented using the **Protocol Deviation** case report form, unless the visit is retrospective.

7. Protocol Deviations

Investigators should not deviate from the study protocol. If a protocol deviation does occur, the deviation must be documented on the **Protocol Deviation** case report form and submitted to the Sponsor. If applicable per their reporting requirements, the Investigator or Designee will also report applicable protocol deviations to their IRB or EC.

8. Study Termination

Study subject participation is expected to end upon completion of the subject's one year follow-up visit unless the subject voluntarily withdraws from the study, is withdrawn from the study by the Investigator, is lost to follow-up, undergoes revision to remove a study device (due to complication), or expires. Reason(s) for study completion must be documented on the **Study Completion** case report form.

If the Sponsor decides to terminate the study early, the Sponsor will inform the Investigators of the reason for early study termination. It is the responsibility of the Investigators to inform their IRB or EC as applicable according to local and national laws/regulations.

9. Modification of the Protocol

All amendments to this clinical protocol shall be agreed to by the Sponsor and be recorded with a justification for the amendment prior to implementation. Approval of the applicable IRB or EC must be obtained prior to implementation, if required according to the local and/or national

laws/regulations.

E. Medical Events/Adverse Events Definitions and Classifications

An adverse event is any unfavorable or unintended sign, symptom, or disease that impacts the subject. Adverse event is synonymous with complication or medical event.

Adverse events are required to be reported on the **Adverse Event Report** case report form. The completed **Adverse Event Report** case report form must be submitted to the Sponsor in a timely manner. The Investigator or Designee will also promptly provide the Sponsor with any additional requested information required for the Sponsor to comply with regulatory requirements. If applicable per their reporting requirements, the Investigator or Designee will also report applicable adverse event(s) to their IRB or EC.

The following definitions are from ISO 14155:2011.

1. Classification of the Event

Adverse Event (AE):

An adverse event is any untoward medical occurrence, unintended disease or injury, or untoward clinical signs (including abnormal laboratory findings) in subjects, users or other persons, whether or not related to the investigational medical device.

Note 1: This definition includes events related to the investigational device or the comparator.

Note 2: This definition includes events related to the procedures involved.

Note 3: For users or other persons, this definition is restricted to events related to investigational medical devices.

Serious Adverse Event (SAE)⁽ⁱ⁾:

A Serious Adverse Event is any adverse event that

- a. led to death
- b. led to serious deterioration in the health of the subject, that either resulted in:
 1. a life-threatening illness or injury, or

2. a permanent impairment of a body structure or a body function, or
3. in-patient or prolonged hospitalization, or
4. medical or surgical intervention to prevent life-threatening illness or injury or permanent impairment to a body structure or a body function

- c. led to fetal distress, fetal death or a congenital abnormality or birth defect.

Note: Planned hospitalization for a pre-existing condition, or a procedure required by the protocol, without serious deterioration in health, is not considered a serious adverse event.

Adverse Device Effect (ADE)⁽ⁱ⁾:

An Adverse Device Effect is an adverse event related to the use of a medical device.

Note 1: This definition includes adverse events resulting from insufficient or inadequate instructions for use, deployment, implantation, installation, or operation, or any malfunction of the medical device.

Note 2: This definition includes any event resulting from use error or from intentional misuse of the medical device.

Serious Adverse Device Effect (SADE)⁽ⁱ⁾:

A Serious Adverse Device Effect is an adverse device effect that has resulted in any of the consequences characteristic of a serious adverse event.

The Sponsor is responsible for determining the final classification of adverse events.

If an Unanticipated Serious Adverse Device Effect (USADE) is identified by the Sponsor, it will be promptly reported to concerned Investigators and regulatory authorities as required by applicable regulatory requirements. If applicable per their reporting requirements, the Investigator or Designee will report the USADE to their IRB or EC.

Device Deficiency:

A Device Deficiency is defined as an inadequacy of medical device with respect to its identity, quality, durability, reliability, safety or performance.

2. Intensity of Symptoms

Mild:

The subject is aware of the sign or symptom, but finds it easily tolerated. The event is of little concern to the subject and/or little clinical significance. The event is not expected to have any effect on the subject's overall health or well-being.

Moderate:

The subject has discomfort enough to cause interference with or change in usual activities. The event is of some concern to the subject's health or well-being and may require medical intervention and/or close follow-up.

